8.6. Data management

Maternal interviews are conducted at enrollment and in each trimester thereafter, depending on the gestational age at which the mother enrolls. An additional outcome interview is conducted by telephone after the end of pregnancy, typically this occurs within 6 weeks but could be up to one year after. These interviews are conducted by telephone and typically take between 30 minutes and 1 hour to complete. The interviews are semi-structured and follow interview data collection forms to ensure that all study questions are addressed. Data from each interview form is entered into the study database at the end of the interview by the same person who conducted the interview. Medical records are requested from the hospital of delivery (maternal and neonatal information), obstetric provider (maternal information), pediatrician (neonatal/infant) and any specialty physician (maternal and neonatal/infant information). When records are received and catalogued, data is abstracted by trained personnel from each record using a standard abstraction form and entered into the study database. Hard copies or electronic copies of all study forms and medical records are retained in the OTIS Research Center at the University of California, San Diego. Several logic checks are built into the study database. In addition, all data entry is validated for a series of predefined critical variables and a random subset are validated for non-critical variables. Access to the database is controlled by password with administrative level access required for certain operations. Hard copies or electronic copies of patient files and subject signed consent forms will be kept in locked file rooms, locked cabinets or locked electronic drives under the supervision of the study investigators.

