Limited data are available from human subjects who received substantial exposure to belimumab during pregnancy, as women who became pregnant in belimumab clinical trials were withdrawn from treatment as soon as the pregnancy was detected through monthly pregnancy screening. However, in a study of prenatal and postnatal development conducted in cynomolgus monkeys, pregnant monkeys received belimumab by IV injection at approximately gestation day 20-22 and every 2 weeks thereafter until parturition [Belimumab Investigator's Brochure [IB], 2020; 2011N128591_06]. Treatment with belimumab was not associated with direct or indirect harmful effects with respect to maternal toxicity, developmental toxicity, or teratogenicity. Treatment-related findings were limited to expected reduction of B cells and IgM in both dams and infants. B-cell numbers recovered after the cessation of belimumab treatment by about 1-year post-partum in adult monkeys and by 3 months of life in infant monkeys. IgM levels in infants exposed to belimumab in utero recovered by 6 months of age. Study data revealed the passage of belimumab across the placenta and excretion of belimumab into the milk of nursing female monkeys. Human Genome Sciences Inc. (HGS) and GlaxoSmithKline (GSK) have completed two Phase 3 studies for the use of belimumab in SLE. In the Phase 3 studies [Navarra, 2011; Furie, 2011] autoantibody-positive patients with active SLE were administered either intravenous (IV) belimumab (1 mg/kg or 10 mg/kg) or placebo in addition to their baseline medications for lupus. Active disease was considered to be a Safety of Estrogen in Lupus Erythematosus National Assessment - Systemic Lupus Erythematosus Disease Activity Index (SELENA-SLEDAI) ≥ 6 . In the Phase 3 studies, belimumab 10 mg/kg plus standard therapy demonstrated superiority over placebo plus standard therapy in reduction in disease activity as measured by the SLE

responder index (SRI) with an acceptable safety profile. Evidence of benefit in other clinical measures such as reductions in disease activity as measured by SELENA-SLEDAI, severe flare, and reduced steroid use were also observed.

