Outcome	General definition	Denominator	Pregnancy involving multiples	Outcome assessment	Exposure time	Endpoints
Serious infections up to one year of age:	Defined infections requiring hospitalization identified in live born infants up to one year of age	Live born infants	Included each counted separately	From birth up to 1 year of age	3 months prior to LMP and/or at any time in pregnancy ³	
Cohort 1: Serious infections identified up to 1 year of age among live born infants, with pregnancy exposure at any time in pregnancy³;
 
Cohort 2: Serious infections identified up to 1 year of age among live born infants, with no exposure at any time in pregnancy³

¹Pregnancy outcomes include ending in live births, spontaneous abortion, elective termination, or stillbirth

²Exposure in the 2nd and 3rd trimester will be considered for those selected major birth defects that are potentially biologically plausibly related to later pregnancy exposures, e.g., craniosynostosis

³Any time pregnancy defined as any exposure from 3 months prior to LMP through the end of pregnancy (see Section 8.3.1 for details)

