Variable	Cohort 1 Belimumab- exposed	Cohort 2 Disease comparison	Case-Series Belimumab- exposed (non- cohort)	Data Collection Time Period
Maternal Interviews⁶				
Belimumab exposure timing	√		√	At every interview
Belimumab dose	√		√	At every interview
Belimumab duration	√		√	At every interview
Pregnancy Outcomes				
Any birth defects	√	√	√	At every interview
Other pregnancy outcomes ⁴	√	√	√	At outcome interview
Infant Outcomes (up to 1 year of age)				
Infant size	√	√	√	At outcome interview
Serious infections	√	√	√	At outcome interview
Developmental concerns ⁸	√	√	√	1 year of age
Potential confounders/effect modifiers				
Maternal/paternal characteristics	√	√	√	At enrollment interview
Self-reported disease severity	√	√	√	At every interview
Previous pregnancy and delivery birth defect history	√	√	√	At enrollment interview
Maternal conditions	√	√	√	At every interview
Other maternal exposures/concomitant medications ¹	√	√	√	At every interview
Maternal lifestyle habits	√	√	√	At every interview
Prenatal testing	√	√	√	At every interview
Pregnancy complications	√	√	√	At every interview
Infant complications and pediatric exposures	√	√	√	At outcome interview
Medical Record Abstraction^{2,7}				
SLE diagnosis validation ⁵	√	√	√	Medical history
Pregnancy validation	√	√	√	Medical history
Belimumab Exposure				
Exposure timing, dose, duration validation	√		√	Preconception to pregnancy outcome
Pregnancy Outcomes				
Major birth defects ^{3,9}	√	√	√	LMP to infant 1 year of age
Other pregnancy outcome validation ⁴	√	√	√	LMP to pregnancy outcome
Infant Outcomes (up to 1 year of age)				
Birth and postnatal growth	√	√	√	Birth to 1 year of age

Variable	Cohort 1 Belimumab- exposed	Cohort 2 Disease comparison	Case-Series Belimumab- exposed (non- cohort)	Data Collection Time Period
Serious infections	√	√	√	Birth to 1 year of age
Minor birth defect patterns ^{3,9}	√	√	√	Birth to time of dysmorphology examination
Potential confounders/effect modifiers				
Clinically assessed disease severity	√	√	√	Preconception to pregnancy outcome dependent on last clinical assessment
Previous pregnancy, delivery birth defect history validation	√	√	√	Medical history
Maternal conditions validation	√	√	√	Medical history
Maternal exposure/concomitant medications ¹ validation	√	√	√	Preconception to pregnancy outcome or within 2 years of LMP for specific exposures
Prenatal testing validation	√	√	√	LMP to pregnancy outcome
Infant complications and pediatric exposures	√	√	√	Birth to 1 year of age

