Infant vaccination status	√	√		Birth to 1 year of age
Birth and postnatal growth	√	√	√	Birth to 1 year of age
Serious infections up to 1 year of age	√	√	√	Birth to 1 year of age

¹ For cohorts 1 & 2 primarily medications used for the treatment of SLE will be assessed.

² Information will be dependent on the completeness of the medical record

³ Performed periodically and before each annual and final study reports

⁴ Includes preterm delivery, spontaneous abortion, elective termination, stillbirth, small for gestational age

⁵ including clinical manifestations such as lupus nephritis if available

⁶ Maternal interviews: can be up to 4 interviews, depending on gestational age at enroll

ment and include: enrollment interview (any time in pregnancy), interim interview I (20-22 weeks gestations), interim interview II (32-34 weeks gestation), and pregnancy outcome interview (0-6 weeks post-delivery)

⁷ Medical record review will occur at 0-12 months post-delivery for pregnancy information and 1 year post-delivery for infant information

⁸ The ASQ-3 will be sent electronically to the participant or, if the participant prefers, a hard copy questionnaire will be mailed for completion.

⁹ Data also collected from the study dysmorphological examination

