8.6.1. Data handling conventions

Major birth defects are classified using the CDC coding manual [CDC, 2017] by the Study dysmorphologist. All defect classifications are reviewed by the Study

Investigators. All prenatal exposures to medications and vaccines are coded using the Slone Drug Dictionary (<http://sites.bu.edu/slone-drug-dictionary/>).

Twins or higher order multiples are handled as one pregnancy outcome. For example, if the pregnancy ends in at least one live born infant, the outcome is considered a live born outcome. If either or both twins have a major birth defect, the outcome is considered one major birth defect outcome. Twins are excluded from analyses of preterm delivery and SGA infants.

Lost-to-follow-up status is designated if a participant withdraws from the study, or if the study staff are unable to make contact with the study participant within 12 months of the estimated end of pregnancy in order to obtain outcome information.

Coding of outcomes is performed by the study staff using the definitions provided in the protocol. The primary source of information on exposure and outcome is the participant. Validation of study outcomes is performed using medical records. In the case of discrepancies in the two sources of report, the participant is recontacted to determine if the discrepancy can be resolved, and a Standard Operating Procedure (SOP) for adjudicating these decisions has been developed.

Missing values for the critical data for OTIS studies are typically very few and nearly always less than 10%. Complete case analysis is planned and there is generally no need to include imputation strategies; however, depending on the prevalence of missingness, sensitivity analyses will be conducted. These will be documented in the SAP.

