to when women would typically enroll in the study. However, based on expected gestational timing of enrollment, spontaneous abortion rates in late first trimester and early second trimester will be analyzable. Further, measurement of a rare outcome may also limit the ability to adjust for potential confounders in multivariable analyses. Where possible due to sufficient events, a propensity score is planned to include relevant confounders.

A bias of this study might be associated with right truncation or censoring. This occurs when pregnancies end the follow-up before the outcome is known (censoring), or with unknown outcomes (truncation). Since pathology is rarely available for spontaneous abortions and terminations for social reasons, most cohorts consider the prevalence of malformations in livebirths rather than the cumulative incidence over gestation. Failure to include defects detected among terminations can underestimate the incidence of malformations and decrease power but, if the missingness is random with respect to exposure, the relative risk for malformations will be unbiased. Additionally, for other outcomes that are also dependent on timing of enrollment in relation to the outcome occurrence (e.g. elective termination and ectopic/molar pregnancy) there may be incomplete data. The dysmorphology exam for minor birth defects may not be performed consistently across all infants and thus there may be missing data for some infants. Medical records may also not be available for all women or infants and there could be missing data from these sources as well. Efforts will be made to enroll a disease comparison group that is of similar disease severity however, there could be differences between the cohorts that may not be able to be adjusted or accounted for due to the nature and collection of the data.

Strengths of the study design are the ability to build on the referral network of OTIS member services across the U.S. and Canada to identify belimumab-exposed pregnancies as well as appropriate comparison group pregnancies, the OTIS research groups' track record of excellent subject retention (<5% lost to follow-up) [[Chambers, 2010](#); [Chambers, 2016](#); [Chambers, 2019b](#)]. In addition, the study design allows for appropriate comparison to a treated disease group, and for appropriate attention to confounding or effect modification.

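### After the outcome interview, normally held by 6 weeks, serious infant infection to 1 year is ascertained from records alone, and sections 8.4, 8.6 and 9.1 do not expressly name a hospital that admits the infant later

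*Protocol*

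**What the plan says.** **Endpoint.** Table 2 (section 8.3.2) gives "Defined infections requiring hospitalization identified in live born infants up to one year of age". The Cohort 1 endpoint reads "Serious infections identified up to 1 year of age among live born infants, with pregnancy exposure at any time in pregnancy". The denominator is live born infants, with no stated condition on having 1-year information.

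**Maternal report.** Table 3 (section 8.4) collects serious infections from the mother at one time point: "At outcome interview". Infant complications and pediatric exposures, which under section 8.3.3 include hospitalizations, are asked at the same single point. Footnote 6 sets the timing: "pregnancy outcome interview (0-6 weeks post-delivery". Table 5 agrees. Section 8.6 says the interview is usually within 6 weeks but may be as late as one year.

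**Later contact.** At 1 year, Table 5 schedules a pediatric record request and review and the ASQ. The ASQ is a developmental screen.

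**Records.** Table 3 also has serious infections abstracted from medical records for birth to 1 year, in both cohorts. Section 8.6 gives the sources: "Medical records are requested from the hospital of delivery (maternal and neonatal information), obstetric provider (maternal information), pediatrician (neonatal/infant) and any specialty physician"; the specialty physician's records there cover infant as well as maternal information. Section 8.4 adds other providers involved in the pregnancy. Section 9.1 names only the pediatrician for the infant's release. The abstract lists hospital providers without qualification.

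**Handling rules.** Section 8.6.1 makes the participant the primary source for outcomes, uses records for validation, and plans complete-case analysis. A woman is lost to follow-up if she withdraws or staff are "unable to make contact with the study participant within 12 months of the estimated end of pregnancy in order to obtain outcome information". Section 8.9 concedes: "Medical records may also not be available for all women or infants".

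**The concern.** The endpoint runs for a year, but its declared primary source normally falls silent after about 6 weeks. For a later admission there is then usually no maternal report for the records to validate, and no discrepancy to prompt recontact. The records become the only source. The one that documents a hospital admission most directly, the admitting hospital's own, is not expressly on the request or release lists. Because the interview may also be held much later, the recall window differs between women.

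The timing matters for a B-cell-directed antibody. In the monkey study cited in section 6.1, infant B cells recovered by 3 months, and "IgM levels in infants exposed to belimumab in utero recovered by 6 months of age". A 6-week interview covers the early part of those windows and not the rest.

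If later admissions are missed, the observed rates fall in both cohorts and the study loses power. If they are missed more often in one cohort, the relative risk moves in either direction. No statistical analysis plan can recover an admission that was never asked about and does not appear in the records obtained.

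**Working it through.** **Plan's own figures.** The protocol states no rate, power or sample size for serious infections, so there is nothing on this endpoint to reproduce. The live-birth numbers in section 8.5 do reproduce: 200 × (1 − 0.10 − 0.05) = 170 and 200 × (1 − 0.15 − 0.05) = 160 per cohort.

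**Coverage by maternal report (timing from Tables 3 and 5).**
- Risk year: at most 6/52 = 11.5%, leaving 46/52 = 88.5%.
- Taking 3 months as 13 weeks: 6/13 = 46%. Taking 6 months as 26 weeks: 6/26 = 23%.

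**Effect of incomplete records (illustrative).** Let *e* be the share of events before the interview. Let *m* be the share of later events that the records fail to show, either because the chart is silent or because no chart arrives and the infant is counted as event-free. The captured share is f = e + (1 − e)(1 − m). Both inputs are assumptions; e = 11.5% corresponds to a constant hazard.

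| e | m = 10% | m = 20% | m = 40% |
|---|---|---|---|
| 11.5% | 0.912 | 0.823 | 0.646 |
| 25% | 0.925 | 0.850 | 0.700 |
| 40% | 0.940 | 0.880 | 0.760 |

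At an assumed true comparator risk of 5%, the observed risk is 0.05 × f, or 3.2% to 4.7%. With 170 per group, two-sided 0.05 and 80% power, the minimum detectable relative risk rises from 2.77 to between 2.85 and 3.41.

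**Relative risk.** It is multiplied by f(exposed)/f(comparator):

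| m exposed / comparator | e = 11.5% | e = 25% | e = 40% |
|---|---|---|---|
| 20% / 20% | 1.00 | 1.00 | 1.00 |
| 10% / 30% | 1.24 | 1.19 | 1.15 |
| 30% / 10% | 0.81 | 0.84 | 0.87 |

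A small difference does little: 5% against 10% at e = 11.5% gives 0.956/0.912 = 1.05.

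**If infants without a chart are excluded instead.** Complete-case analysis removes that part of *m* and costs numbers: 170 × 0.90 = 153, or 170 × 0.60 = 102, at 10% or 40% without charts, taking one infant per pregnancy. It does not help where a chart arrives but omits the admission.

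**The case against.** The strongest reply is that the whole risk year is scheduled for observation. Table 3 abstracts serious infections from birth to 1 year, Table 5 requests pediatric records at 1 year, and both apply equally to the two cohorts. That stands. A reader might infer from Table 3 that infections are sought only up to 6 weeks; that is true of scheduled maternal report, not of the study, and section 8.6 allows a later interview.

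A reader might also infer that admitting-hospital records are never requested. The text does not go that far. The abstract's hospital is not limited to delivery, specialty records include infant information, and a pediatric chart may mention an admission. What remains is that the three operative lists do not expressly name that hospital.

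A third tempting inference is that infants with no later data are counted as infection-free. No section says so. Complete-case analysis points the other way, live born infants is a population label shared with the 1-year growth and ASQ outcomes, and the definition of evaluable infants may be in the statistical analysis plan. Still, the lost-to-follow-up rule would not by itself remove an infant whose mother gave an early interview, and Table 2 does restrict minor defects to infants who were examined. Clarifying the point is reasonable; alleging a coding error is not.

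The animal findings are not stated to be the reason for this endpoint, and the first 6 weeks lie inside both recovery windows. Section 8.9 already discloses that records may be missing, but disclosure adds no data.

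**Conclusion.** The point holds as a weakness in data collection for one secondary safety endpoint. Maternal report covers at most 11.5% of the risk year when the interview is held on schedule. The other 88.5% depends on pediatric and specialty records of unstated completeness, and a later admitting hospital is not expressly listed.

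The probable direction is understated rates in both cohorts. Bias in the relative risk needs unequal completeness, for which the protocol gives no evidence; the multipliers of 0.81 to 1.24 show sensitivity to assumed gaps of 10% against 30% and are not estimates. The primary outcome is unaffected. The change is worth making now because it concerns what is collected.

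**What to change.** 1. At the existing 12-month ASQ contact, ask mothers in both cohorts about infant hospital admissions and infections since the last interview, and add this to Tables 3 and 5.
2. Add any hospital that admits the infant in the first year to the record request and release lists in sections 8.4, 8.6 and 9.1.
3. In the serious-infection endpoint cell of Table 2, limit the analysis to infants with a 1-year record or 12-month contact, as the minor-defect row does for examined infants, or censor at the last date covered. Report coverage by cohort.

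Cost: protocol wording, a few questions at a contact already scheduled, one more line on the release form, and occasional extra record requests. No new visit is needed. Restricting the analysis may reduce the number of infants, which is why coverage should be shown.

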8.6.1. Data handling conventions

Major birth defects are classified using the CDC coding manual [CDC, 2017] by the Study dysmorphologist. All defect classifications are reviewed by the Study

Investigators. All prenatal exposures to medications and vaccines are coded using the Slone Drug Dictionary (<http://sites.bu.edu/slone-drug-dictionary/>).

Twins or higher order multiples are handled as one pregnancy outcome. For example, if the pregnancy ends in at least one live born infant, the outcome is considered a live born outcome. If either or both twins have a major birth defect, the outcome is considered one major birth defect outcome. Twins are excluded from analyses of preterm delivery and SGA infants.

Lost-to-follow-up status is designated if a participant withdraws from the study, or if the study staff are unable to make contact with the study participant within 12 months of the estimated end of pregnancy in order to obtain outcome information.

Coding of outcomes is performed by the study staff using the definitions provided in the protocol. The primary source of information on exposure and outcome is the participant. Validation of study outcomes is performed using medical records. In the case of discrepancies in the two sources of report, the participant is recontacted to determine if the discrepancy can be resolved, and a Standard Operating Procedure (SOP) for adjudicating these decisions has been developed.

Missing values for the critical data for OTIS studies are typically very few and nearly always less than 10%. Complete case analysis is planned and there is generally no need to include imputation strategies; however, depending on the prevalence of missingness, sensitivity analyses will be conducted. These will be documented in the SAP.

8.6.2. Resourcing needs

Not applicable.

8.6.3. Timings of Assessment during follow-up

Table 5 Timing of Cohort Enrollment, Interviews, 2 Medical Records

	Any Time in Pregnancy	20-22 Weeks' Gestation	32-34 Weeks' Gestation	0-6 Weeks Post-Delivery	0-12 Months Post-Delivery	1 Year Post-Delivery
Referral	√					
Enrollment and Consent	√					
Enrollment Interview	√					
Interim Interview I		√				
Interim Interview II			√			
Pregnancy Outcome Interview and Request for Medical Records*				√		
Pregnancy Medical Record Review					√	
Pediatric 1-Year Medical Records Request and Review						√
Pediatric 1-Year ASQ						√

*Contact earlier if pregnancy outcome occurs earlier

